3.1. Study design

Randomized triple-blinded multicentric clinical trial, conducted in parallel, with two arms:

The trial will be performed with health care workers (Physicians, Nurses, Respiratory therapists, or nurse assistants) free of SARS-CoV-2 infection prior, recent or at the time of the inclusion and who directly care for confirmed or suspected cases of COVID-19 in the emergency room, general COVID wards or intensive care units. A screening at baseline will be carried out in order to evaluate for eligibility by performing: SARS-CoV-2 RT-PCR, SARS-CoV-2 IgG antibodies, as well as, hemogram, creatinine, serum phosphorus, AST, ALT, ELISA for HIV, surface Hepatitis B antigen antibodies, qualitative pregnancy test (b-HCG). Once

eligibility is verified participants will be randomly assigned to either an intervention or a control group.

The interventions consists in the administration of Tenofovir/ Emtricitabine (300 mg / 200 mg daily during 60 days) + Personal Protective Equipment (PPE) and the control consists in the administration of placebo (1 tablet daily during 60 days) + Personal Protective Equipment (PPE)

All participants will have PPE recommended for the preventions of COVID-19 by the WHO which include mayo dress, nonfluid long sleeve gown, ocular protection with goggles, face shield or visor and surgical mask in procedures that do not aerosolize. N-95 respirators are required for procedure that generate aerosols. For detailed description see Table 2.

The re-use of N-95 respirators will be allowed according to CDC and WHO guidelines. This taking into consideration the shortage of supplies for the actual situation. The N-95 continuous use will be for 8 hours and the N-95 intermittent use will be allowed up to 5 times with the precaution of storage in a paper and plastic bag label them with the participant name and placed them in a plastic recipient at the end of shifts(48).

After baseline evaluation and confirming eligibility an initial visit and 4 follow up visits at day 20, 40, 60, 75 days will be carried out. See Table 1 and Graph 1.

In the case of presenting COVID-19 related symptoms at any time after enrolling a SARS-CoV2 RT-PCR will be performed between day 1 to 5 of the onset of symptoms and will be repeated it after 72 hours in case that the first one is negative. In the case of having any positive SARS-CoV2 RT-PCR or SARS-CoV2 IgG SARS-CoV2 infection will be confirmed and the intervention will be suspended.

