3.5. Duration of the study and time of termination

- Duration of the interventions: 60 days
- Total duration of the Project: 8 months
 - ✓ 2 months planning, 5 months collecting data, 2.5 months recruiting and a month for data analysis and publication.

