3.6.7. Study variables

The study variables are in Annex 3 with their respective conceptual and operational definitions.

3.6.8. Sample processing and interpretation of laboratory tests.

- RT-PCR: it will be processed in the HUSI clinical laboratory for the volunteers of the HUSI, the National University Hospital and the Samaritana Hospitals; The centers of the Colsanitas Group will perform the PCR in the Colsanitas group laboratory and the PCR of the San Jorge Hospital at the

Technological University of Pereira according to the protocols used in each of these institutions, with internal and external quality controls, as well as technical endorsed by the National Institute of Health. The results will be sent within 24 hours after taking the sample to the doctors assigned to the study, who will inform the patient and carry out the pertinent follow-up. (See Annex 6. Diagnostic tests)

- Serological tests for IgG antibodies will be processed in the HUSI clinical laboratory and the Colsanitas Group centers. The qualitative detection of IgG antibodies against SARS-CoV-2 will be carried out in human serum or whole blood obtained from the volunteers, using the immunochromatography test: Standard Q, SD Biosensor®. The antibodies present in the sample form a complex with the antigen labeled with colloidal gold (SARS-CoV-2 recombinant antigen), the complex progresses under the action of chromatography and combines with the coated antibody (mouse monoclonal antibody IgM / IgG anti-human) in the IgG line to form a complex and develop color, which is a positive result. When the sample does not contain the SARS-CoV-2 IgG antibody, the complex cannot form and a red band does not appear on the IgG line, which is a negative result. Regardless of whether either SARS-CoV-2 IgG or IgM antibodies are present in the sample, the gold-labeled quality control antibody will bind to the coated antibody on line C to form a complex and develop color (line C) to validate the test. For the study, only IgG antibody results will be considered, contemplating the high rate of false positives of IgM tests, especially in asymptomatic patients (66).

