3.6.9. Procedure in case of presenting the primary outcome

If the volunteer, after the start of the study, has a positive result of RT-PCR or IgG for SARS CoV2, which confirms the infection by COVID 19, they will be contacted virtually or in person. During this intervention, the following actions will be carried out:

- You will be given information about your result, and you will be instructed to contact your occupational risk and health insurer.
- The presence of alarm signs (drowsiness, dyspnea, cyanosis) will be evaluated. In case of any of these symptoms are present, the patient will be instructed to attend the emergency service, to receive treatment in accordance with current national and institutional guidelines.
- The volunteer will be instructed to suspend the intervention product, and the masking will be released.
- National Public Health Surveillance System mandatory notification form will be filled out, the institution where the volunteer works will be informed, and the completed form will be sent.

- The volunteer will be informed that telephone follow-up will be carried out every 5 days until the symptoms are resolved or a maximum of six weeks after the diagnosis of COVID 19. In case of presenting any alarm sign during the follow-up, the patient will be recommended to attend the emergency department.

During the telephone follow-up, the volunteer's primary outcome (COVID 19 infection) will be classified as follows: asymptomatic, mild, moderate, or severe COVID. If the patient does not answer due to physical impossibility (e.g. intubation), communication with a companion or family member previously authorized by the patient will be sought.

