The hazard ratio will be estimated by comparing the risk of infection in the intervention group (TDF/FTC + EPP), with the risk in the control group (placebo + EPP), with a confidence interval of 95 %, using a univariate Cox regression model.

If necessary, adjustment will be made for variables that may affect the occurrence of the primary outcome and that are not balanced between the intervention group and the placebo group; The need for adjustment with an OR greater than 1.5 will be considered for dichotomous categorical

variables, such as sex; or if there are differences between the groups greater than 0.25 of the standard deviation for continuous variables such as age, adherence to pharmacological intervention or EPP, and hours of exposure to the COVID area. For the calculation of the adjusted hazard ratio, a multivariate Cox proportional hazards model will be used, if the proportionality assumption is met, or an extended Cox model if this assumption is not met.

For secondary outcomes

-The proportion of incidence of total adverse effects in each group will be determined at day 60 after randomization, estimated as the cumulative incidence using the Kaplan Meier method.

The hazard ratio ("Hazard Ratio") will be estimated by comparing the risk of adverse events in the intervention group (TDF/FTC + EPP), with the risk in the control group (placebo + EPP), with a confidence interval of 95%, using a univariate Cox regression model.

Additionally, the same analysis will be performed for serious adverse events.

- The proportion of incidence of discontinuation of the intervention in each group, for any reason, will be determined at day 60 after randomization, estimated as the cumulative incidence using the Kaplan Meier method.

The hazard ratio will be estimated by comparing the discontinuation of the intervention in the intervention group (TDF/FTC + EPP), with the risk in the control group (placebo + EPP), with a confidence interval of 95 %, using a univariate Cox regression model.

- It will be determined as the difference in the mean or median (according to the distribution of the data) of the percentage in which the individuals were adherent

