6.1. Definitions

- Adverse event (AE)

Any adverse medical occurrence in a patient or subject of a clinical investigation to whom a pharmaceutical product was administered and that does not necessarily have a causal relationship with this treatment. Therefore, an adverse event (AE) can be any unfavorable and unintended sign (including an abnormal laboratory finding), symptom or illness temporarily associated with the use of a medicinal (research) product, whether it is related. (104).

Considering the above, the United States National Institute of Health in conjunction with the National Cancer Institute of the same country published standardized definitions of adverse events known as Common Terminology Criteria for Adverse Events (CTCAE). Events, for its acronym in English), to describe the severity of the organic damage caused to patients by the various medications (104,105). According to them, the following events are considered:

- Serious adverse event (SAE)

Any unfavorable occurrence than at any dose that:

- Results in death.
- Is life threatening, requires hospitalization of the patient or prolongation of existing hospitalization.
- Results in persistent or significant disability / disability.
- Generates a congenital anomaly / birth defect.

- Fatal Serious Adverse Event.

EAS that end in the death of the subject or threaten the life of the same.

- Expected / Listed Serious Adverse Event.

EAS whose specificity or severity is consistent with that described in the Research Protocol, Investigator's Manual / basic prescription information or product label.

- Unexpected / Unlisted Serious Adverse Event.

EAS whose specificity or severity is not consistent with that described in the Research Protocol, Investigator's Manual / basic prescription information or product label.

- Non-Serious adverse event

All other events that do not meet any of the EAS seriousness criteria

- Adverse event requested

They are the AE that will be searched for in each assessment of the subjects participating in the study.

- Unsolicited adverse events

They are the AEs that are voluntarily manifested by the patient that may or may not be related to the study drug.

6.2. Assessment and documentation of adverse events.

The researcher assigned to follow up the study subjects will be responsible for recording all adverse events in each participating institution, regardless of the group evaluated, with the following exceptions:

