COVID-19 related symptoms	Qualitative/dichotomous	Development of any of the following symptoms: - Fever: body temperature higher than 38°C - Acute cough (start within the last 10 days) - Shortness of breath - Rhinorrhea - Sore throat - Malaise - Acute diarrhea - Anosmia or hyposmia - Dysgeusia - Headache	0- No symptoms 1- Fever 2- Acute cough 3- Shortness of breath 4- Rhinorrhea 5- Sore throat 6- Malaise 7- Acute diarrhea 8- Anosmia or hyposmia 9- Dysgeusia 10- Headache 11- Other, Specify
Date of symptom start	Quantitative/continuous	Date of start of first COVID-19 related symptom. If no symptoms register 00/00/00.	Day/Month/Year
Adverse event (AE)	Quantitative/nominal	Any untoward adverse event during administration of investigational product that may or may not have a causal relationship with it.	0-No 1-Yes
Serious adverse event (SAE)	Qualitative/nominal	Any adverse event that: - Results in death. - Threatens life and requires hospitalization or prolongation of hospitalization. - Results in permanent or prolonged inability or disability. - Causes congenital defects or malformations.	0-No 1-Yes
Serious adverse event classification	Qualitative/nominal	Expected SAE: An AE whose nature and severity is consistent with what is described in investigator's brochure or drug insert. Unexpected SAE: An AE whose nature and severity are not consistent with what is described in investigator's brochure or drug insert.	1- Expected serious adverse event 2- Unexpected serious adverse event
Fatal SAE	Qualitative/nominal	SAE that results in death	0- No 1- Yes
Type of SAE	Qualitative/nominal	Type of SAE the volunteer developed	1- Acute kidney injury 2- Proximal tubulopathy 3- Emesis 4- Abdominal pain 5- Headache 6- Insomnia 7- Diarrhea 8- Hypersensitivity skin reaction 9- Steven-Johnson's syndrome 10- Maculopapular rash 11- Appendicitis 12- Pancreatitis 13- Other, specify
Date of SAE start	Quantitative/continuous	Date when SAE started	Day/Month/Year
Date of SAE end	Quantitative/continuous	Date when SAE ended	Day/Month/Year

Non serious AE	Qualitative/nominal	Whether volunteer developed non serious AE	0- No 1- Yes
Type of non-serious AR	Qualitative/nominal	Type of non serious AE that volunteer developed	1- Nausea 2- Headache 3- Abdominal pain 4- Flatulence 5- Weakness or tiredness 6- Insomnia 7- Fatigue 8- Vomiting 9- Maculopapular rash 10- Steven-Johnson's syndrome 11- Allergic skin reaction 12- Other, specify

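### Appendix 3 limits adverse events to time on product, section 4 analyses them to day 60 after randomization, and no rule says which window or censoring applies after an early stop

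*Combined protocol and SAP*

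**What the plan says.** Section 3.6.7 gives Appendix 3 its authority: "The study variables are in Annex 3 with their respective conceptual and operational definitions". In Appendix 3 the AE variable for follow-ups 1 to 3 reads "Any untoward adverse event during administration of investigational product that may or may not have a causal relationship with it". The SAE variable is built as a subset of AEs, so it carries the same limit.

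Section 4, under secondary outcomes, uses a different window: "The proportion of incidence of total adverse effects in each group will be determined at day 60 after randomization", by Kaplan-Meier and a univariate Cox model. For SAEs it adds: "Additionally, the same analysis will be performed for serious adverse events".

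Section 6.1 is wider than Appendix 3 and speaks of a "symptom or illness temporarily associated with the use of a medicinal (research) product", with no requirement that product still be taken. Section 6.2 makes the researcher responsible for all AEs. It announces exceptions, but none are listed in the text available. Table 6 marks the AE registry at visits 1 to 4. Table 1 and the follow-up 4 fields of Appendix 3 list no AEs at day 75.

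On stopping, section 3.5 gives "Duration of the interventions: 60 days". Section 3.1 says "In the case of having any positive SARS-CoV2 RT-PCR or SARS-CoV2 IgG SARS-CoV2 infection will be confirmed and the intervention will be suspended", and section 3.6.9 (procedure in case of presenting the primary outcome) says "The volunteer will be instructed to suspend the intervention product, and the masking will be released". Section 3.6.9 (study withdrawal criteria) lists further reasons for leaving early.

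**The concern.** For a participant who completes the course, the two windows nearly coincide. For one who stops early they do not. Under Appendix 3 counting ends at the stop; under section 4 the participant belongs to the comparison until day 60. One reason for stopping is the primary outcome itself, so time off product may differ by arm if the drug works.

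The clearest consequence is for SAEs. A participant who tests positive, stops product and is then admitted has an SAE under section 6.1 but not under Appendix 3. The same holds for a renal or hepatic abnormality found after the stop.

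The dataset also makes this hard to repair afterwards. Neither the product-withdrawal codes nor the interruption codes in Appendix 3 include infection, and the withdrawal date is recorded only when a withdrawal code applies. The date of an infection stop would have to be inferred from test dates. The trial has no data monitoring committee (section 4.1), which is a further reason for the SAE definition to be unambiguous.

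**Working it through.** **Inputs from section 3.4.** Infection risk 0.10 on placebo and 0.05 on active; 475 per arm; observed two-month incidence at the sites 3.3% to 13.7%. The plan states no AE rate and no AE power, so it has no AE figure to reproduce. Its sample size does reproduce approximately: (1.960 + 0.842)² × (0.10 × 0.90 + 0.05 × 0.95) / 0.05² = 431.7 per arm, against the stated 429.

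**Infection stops.** 475 × 0.10 = 47.5 on placebo and 475 × 0.05 = 23.75 on active, if the whole risk falls within 60 days. Section 4 measures the outcome at day 75. If the risk is spread over 75 days at a constant rate, stops by day 60 are 38.4 and 19.1.

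**Share of the 60 days after an infection stop.** With constant hazard l = −ln(1 − p)/60, the share is 1 − (1 − e^(−60l))/(60l). This gives 5.1% on placebo and 2.5% on active (4.1% and 2.0% if risk is spread over 75 days). Across the site range, halving the risk on active, it runs from 1.7% and 0.8% to 7.0% and 3.5%.

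**Effect on the AE comparison if post-stop events are not counted and stopped participants stay at risk.** Assume the same true day-60 AE risk q in both arms, AEs independent of infection, and infection as the only reason for stopping. With m = −ln(1 − q)/60, the counted risk is c = m/(m + l) × (1 − e^(−60(m + l))). The apparent hazard ratio is ln(1 − c_active)/ln(1 − c_placebo).

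| Assumed true risk | Counted, placebo | Counted, active | Gap (points) | Apparent HR |
|---|---|---|---|---|
| 20% | 19.0% | 19.5% | 0.5 | 1.03 |
| 40% | 38.1% | 39.1% | 0.95 | 1.03 |
| 60% | 57.4% | 58.7% | 1.3 | 1.04 |

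At q = 20%, for example, the placebo figure is 0.2231/(0.2231 + 0.1054) × (1 − 0.80 × 0.90) = 0.190. For event risks of 1% to 2% the apparent hazard ratio is also 1.03. The sampling error of the difference is larger than the gap: √(2 × 0.40 × 0.60/475) = 3.2 points at 40%.

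**The same data with AE time censored at the stop.** Under the same independence assumption, Kaplan-Meier and Cox recover the true risk and a hazard ratio of 1.00, so the undercount disappears. What remains is whether those censored at infection have the same later AE risk as those not censored.

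**SAEs after an infection stop.** The share of infections admitted after the stop is not in the documents. Over an assumed 2% to 20%, the admissions outside the Appendix 3 window are 47.5 × 0.02 = 1.0 to 47.5 × 0.20 = 9.5 on placebo, and 0.5 to 4.8 on active.

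**The case against.** The strongest reply is that Appendix 3 is loosely worded and data collection is broader. Section 6.2 and Table 6 call for all AEs to be recorded. Infected participants are telephoned every five days for up to six weeks, and Appendix 3 keeps their severity, hospital, ICU and vital-status data. This stands: a reader might infer that post-stop events are lost, but the documents show only that they fall outside one of two competing definitions.

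A reader might also infer that the drug will look less safe than it is. That is not supported, for three reasons.

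- Section 4's only follow-up rule, written for the primary outcome, ends at infection and censors withdrawals. Carried over to AEs, it removes the undercount.
- Stops for AEs, renal findings, interacting drugs or personal choice have no stated rate by arm. A stop caused by an AE loses no first AE.
- COVID-19 symptoms before the stop may themselves count as AEs. Symptom-driven testing requires two or more symptoms, and product generally continues while the result is pending. With the 18% to 46.5% asymptomatic range in section 1.3, 53.5% to 82% of infections would be symptomatic: 5.4 to 8.2 per 100 on placebo and 2.7 to 4.1 on active. Even after overlap with other AEs, this could offset or reverse the small gap in the table.

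Nor do the documents say that infected participants miss the day-60 laboratory panel. Neither Table 1 nor section 3.6.9 cancels it.

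Finally, an on-treatment safety window is a legitimate choice, and events after an infection stop are assessed with masking released. That supports showing an on-product analysis; it does not settle which window section 4 means.

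**Conclusion.** The conflict is firm: the governing variable list stops counting AEs and SAEs with product, the analysis section runs to day 60 by randomized group, and no AE censoring rule connects them. For AEs overall the numerical effect is small: an apparent hazard ratio of about 1.03 to 1.04 when the truth is 1.00. That figure rests on the planned 10% and 5% risks accruing evenly over 60 days, infection stops only, AEs independent of infection, and stopped participants kept at risk. It would be smaller if infections accrue over 75 days or are first found at the day-60 or day-75 tests. The net direction over all stops is not established. If time is censored at the stop, the question is possible informative censoring rather than undercount. The practical weight lies with SAEs after infection, where a few events could enter or leave the comparison according to which definition is used. This is a low-cost clarification and leaves the sample size unchanged.

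**What to change.** - Make the AE and SAE window in Appendix 3 match section 4: first dose to day 60 after randomization, whether or not product is still being taken, for participants who still consent. Use the same definition in section 6.
- State in section 4 how AE and SAE time is censored, in particular at infection, product stop and withdrawal of consent.
- Record the date and reason of every product stop, adding infection as a reason, and add an on-product flag to each AE.
- Report on-product AEs and non-COVID AEs as labelled sensitivity analyses.
- State that the safety tests already in the schedule still apply after a product stop, for those who still consent.

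The cost is wording in three places, small eCRF additions, and tests already planned. The downside is that off-product events, including COVID-19 illness that may differ by arm, enter the main count. The flag identifies off-product events and the sensitivity analyses show their influence.

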3.6.9 Study withdrawal criteria

The following criteria should determine the immediate withdrawal of the volunteer from the study:

- Grade 2 or greater kidney abnormalities at any time of follow-up.
- Clinical indication to start a drug with significant interactions with TDF/FTC during the development of the study.
- Presentation of any serious adverse event related to the intervention, defined by the physicians assigned to the study.
- Any Adverse Event (AE) that determines that the volunteer wishes to interrupt the intervention.
- That the volunteer voluntarily and for any reason decide to withdraw from the study.

If any of the previously mentioned criteria are met, the doctor assigned to the study in charge of the follow-up will immediately inform the coordinator of their respective center. The report of all AE will be made by the principal investigator of each center, in accordance with the INVIMA regulations and taking into account the Standardized Operating Procedures (SOP) established by the study.

In the event that the patient withdraws their consent, no additional monitoring will be possible. This situation will be reported immediately to the clinical monitor and monthly to the Institutional Research and Ethics Committee (CIEI).

3.6.10. Follow-up of volunteers with a positive pregnancy test at the end of follow-up

Despite the fact that TDF/FTC is a classification B drug in pregnancy, and its use is recommended as one of the antiretrovirals of choice in pregnant women with HIV (76), within this study it was defined to exclude pregnant women, or with the desire to become pregnant, to avoid exposure to this drug given its high placental transfer to the fetus.

There is no evidence in humans of teratogenicity with TDF/FTC, however there is evidence in monkeys, at doses twice as high as the therapeutic doses in humans, of decreased fetal growth and reduced fetal bone porosity within two months of initiation of maternal therapy; Regarding human studies, there is no demonstrated relationship with low birth weight, but there are conflicting results on the outcome of growth in childhood (77).

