A case report form will be created which must have the following information:

- Description of the adverse event
- Date of presentation, duration, and day of resolution.
- Severity according to degrees mentioned
- Conduct taken (need for treatment, suspension of medication, hospitalization)
- The probability of relationship with the drug under study.

All the follow-up of adverse events will be determined according to the Standardized Operational Plan for adverse events of the study.

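### Appendix 3 requires an SAE to be both life-threatening and hospitalised where section 6.1 lists alternatives, so the SAE flag could under-count

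*Combined protocol and SAP*

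**What the plan says.** Section 6.1 (Definitions) lists what makes an event serious. Apart from death, disability and congenital defect, one bullet reads "Is life threatening, requires hospitalization of the patient or prolongation of existing hospitalization". The comma and the single closing conjunction make this a list of alternatives. An event that meets no criterion falls into the non-serious class: "All other events that do not meet any of the EAS seriousness criteria".

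Appendix 3, which section 3.6.7 makes the home of the study variables and their definitions, words the same criterion as "Threatens life and requires hospitalization or prolongation of hospitalization".

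The two places also differ on Fatal SAE. Section 6.1 has "EAS that end in the death of the subject or threaten the life of the same"; Appendix 3 has "SAE that results in death".

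Two parts of the plan use the SAE classification:

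- Section 4, secondary outcomes, sets out a Kaplan-Meier cumulative incidence at day 60 and a univariate Cox hazard ratio for adverse events, then adds: "Additionally, the same analysis will be performed for serious adverse events".
- The study withdrawal criteria (section 3.6.9) include "Presentation of any serious adverse event related to the intervention, defined by the physicians assigned to the study". Appendix 3 carries a matching withdrawal variable, and section 4 censors the primary outcome when any withdrawal criterion is met.

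Hospitalisation is also captured elsewhere. The case report form in section 6.2 records, for each adverse event, "Conduct taken (need for treatment, suspension of medication, hospitalization". For COVID-19 cases, Appendix 3 has a severity category and dates of hospital and ICU admission and discharge.

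**The concern.** Seriousness criteria are normally read as a list in which any one suffices, and section 6.1 is written that way. Joining two of them with a conjunction narrows the class. An admission for an event that does not threaten life would be serious on one page and non-serious on the other, and so would a life-threatening event managed without admission.

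At stake is the count of SAEs in a planned between-arm safety comparison and, for related events, whether the participant meets a withdrawal criterion and is censored. Section 4.1 decides against a data monitoring committee, so no independent body would be reviewing accumulating SAE classifications. That leaves the definition on the form to do more of the work.

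**Working it through.** The documents give no figure to reproduce, so the check compares the two texts and then applies a formula with one assumed input.

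**Step 1. The logic.** Let A be threat to life and B be hospitalisation or its prolongation. Consider only events that do not already qualify by death, disability or congenital defect.

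| Event | Section 6.1 (A or B) | Appendix 3 (A and B) |
|---|---|---|
| A and B | serious | serious |
| B without A | serious | non-serious |
| A without B | serious | non-serious |
| neither | non-serious | non-serious |

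The Appendix 3 phrase could also be parsed so that prolongation alone qualifies. That would not rescue a new admission without threat to life, nor a threat to life without admission.

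**Step 2. The protocol's own grading keeps A and B apart.** In Table 4, hospitalisation is a grade 3 feature of vomiting and of allergic reaction, and threat to life is grade 4 for both. So the B-without-A row is a category the protocol itself recognises.

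**Step 3. The SAE list on the form.** The Type of SAE variable in Appendix 3 names 12 types plus an open category. Four of the 12 (abdominal pain, headache, insomnia, maculopapular rash) have no grade 4 or 5 in Table 4. Under a literal A-and-B rule these could hardly ever be recorded as serious, although the form offers them.

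**Step 4. The size, as a function of an assumption.** Let q be the share of hospitalised adverse events that are also life-threatening. Section 6.1 counts all of them and Appendix 3 counts q of them. Share dropped = 1 - q.

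| Assumed q | Share of hospitalised adverse events dropped |
|---|---|
| 0.1 | 1 - 0.1 = 90% |
| 0.5 | 1 - 0.5 = 50% |
| 0.9 | 1 - 0.9 = 10% |

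The documents give no value for q. Life-threatening events without admission would add to the loss, and no figure is given for these either.

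**Step 5. Can the flag be rebuilt?** The section 6.2 form holds the date of presentation and whether the participant was hospitalised, so in principle it can. The Appendix 3 list alone would not suffice. It gives start and end dates only for SAEs; for non-serious events it has yes/no, type and grade, and its hospitalisation dates sit with COVID-19 severity. A reconstructed time-to-event analysis would depend on the section 6.2 form.

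**The case against.** A reader might infer that the eCRF would miss most hospitalisations. The documents do not support this, for two reasons. First, the admissions are still recorded, on the section 6.2 form and, for COVID-19, in their own variables; what may be wrong is the seriousness flag. Second, most would require q below 0.5, and nothing in the documents says where q lies.

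A reader might also infer a biased safety hazard ratio. That is not shown. Participants are individually randomised, and section 3.6.6 keeps investigators blind, so whichever wording a site follows applies to both arms. The likely harm is fewer counted events and lower precision. One qualification is that masking is released after a positive test (section 3.6.9), so the blinding argument is strongest for events before infection.

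The best case for leaving the text alone is that the conjunction is a slip, perhaps of translation, since untranslated Spanish remains in the document. The phrase stands in the conceptual column, and the operative entry is only a yes/no code. The SAE list in Step 3 suggests that hospitalisation alone was meant to qualify. Sites also have an investigator's manual, SOPs, training, monitoring and audits, none of which can be seen here, and the related-SAE criterion leaves room for the study physicians' judgement. No analysis in section 4 uses Fatal SAE.

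Much of this stands. It makes a literal application less certain and the intended meaning easier to guess. It does not remove the conflict: a yes/no code has no content apart from the definition beside it, and the plan does not say which text governs.

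**Conclusion.** The conflict is real and should be resolved. Read literally, the Appendix 3 flag would classify non-life-threatening admissions, and life-threatening events without admission, as non-serious unless another criterion applies. The planned SAE cumulative incidence and hazard ratio, and the related-SAE flag for withdrawal and censoring, could then under-count.

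The conclusion about the texts is firm. The size is not known: it depends on how far sites follow Appendix 3 rather than section 6.1, and on q, for which the range above is only illustrative. The consequence to expect is misclassification with some loss of events and precision, not lost admissions and not a demonstrated bias between arms. The Fatal SAE mismatch is a smaller matter of the same kind: a survivor of a life-threatening event is a fatal case under section 6.1 and not under Appendix 3.

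**What to change.** - In the SAE row of Appendix 3 and on the eCRF, list threat to life and hospitalisation or its prolongation as separate alternatives, any one sufficient, matching section 6.1. Splitting the single bullet in section 6.1 the same way would remove any doubt.
- Use one definition of Fatal SAE, death only, in both places. Threat to life remains a seriousness criterion in its own right.
- Check that the investigator's manual and SOPs carry the same wording. If events have already been coded, re-derive the flag from the section 6.2 form before the allocation code is revealed.

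The withdrawal rule itself is not at issue here; it only needs to rest on one SAE definition. The cost is a wording change in Appendix 3 and section 6.1 and new eCRF labels, with no effect on sample size, visits or the analysis model.
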